6.1. Inclusion Criteria

Patients are eligible to be included in the study only if they meet all of the following criteria at screening or as specified:

Type of Patient and Disease Characteristics

- [1] Have an established diagnosis of r-axSpA with sacroiliitis defined radiographically according to the mNY criteria (van der Linden et al. 1984) based on central reading: sacroiliitis grade ≥ 2 bilaterally or grades 3 to 4 unilaterally.

AND

At least 1 SpA feature, according to ASAS criteria (Rudwaleit et al. 2009; Sieper et al. 2009), listed in Appendix 5.

- [2] Patients have a history of chronic back pain ≥ 3 months with age at onset < 45 years.
- [3] Have active r-axSpA defined as BASDAI ≥ 4 and total back pain ≥ 4 (Sieper et al. 2009, Box 25 Spinal Pain) on an NRS at screening and baseline.
- [4] Biologic naïve or have had prior treatment with 1 TNF inhibitor. The TNF inhibitor experienced patient must have discontinued TNF inhibitor due to either intolerance or an inadequate response and have elevated baseline CRP (defined as: In the opinion of the investigator, the patient had an inadequate response to at least 12 weeks of treatment with a TNF inhibitor at an adequate dose and baseline CRP $> 5.00\text{mg/L}$). Biologic naïve patient would be enrolled regardless of the CRP level.

Note: The following washout periods prior to baseline randomization must be followed: etanercept ≥ 28 days; infliximab, adalimumab, or certolizumab pegol ≥ 60 days; golimumab ≥ 90 days.

- [5] Must have had an inadequate response, as determined by the investigator, to 2 or more NSAIDs at the therapeutic dose range for a total duration of at least 4 weeks OR have a history of discontinuation due to intolerance to ≥ 2 NSAIDs.
- [6] Patients must have a history of prior therapy for axSpA of at least 12 weeks prior to screening. Examples of prior therapy may include but are not limited to physical therapy, NSAID, and TNF inhibitor treatment.
- [7] If taking NSAIDs or cyclooxygenase-2 (COX-2) inhibitors, the dose must be stable for at least 2 weeks prior to baseline randomization.

Patient Characteristics

- [8] Are ambulatory male or female patients ≥ 18 years of age at time of screening.
- [9] Must agree to use a reliable method of birth control:

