5.2. Method of Assignment to Treatment

Patients who meet all criteria for enrollment will be randomized to double-blind treatment at Week 0 (Visit 2). Assignment to treatment groups will be determined by a computer-generated random sequence using an interactive web-response system (IWRS). The IWRS will be used to

assign double-blind investigational product to each patient. Site personnel will confirm that they have located the correct assigned investigational product package by entering a confirmation number found on the package into the IWRS.

To achieve between-group comparability, the randomization will be stratified by baseline CRP (non-elevated or elevated) and TNF inhibitors experienced or naïve. The study will enroll approximately 60% of patients with baseline CRP elevated (>5.00 mg/L) and approximately 40% of patients with non-elevated baseline CRP. At least 61 bDMARD-naïve patients will be enrolled per arm.

Once a specific stratum is fully enrolled, the sponsor may stop further enrollment of patients fitting the criteria of that stratum.

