6.4. Multiple Comparisons/Multiplicity

The following is a list of primary and major secondary outcomes to be tested at Week 16:

Primary - proportion of patients achieving an ASAS40 response in bDMARD-naïve patients [ASAS40 naïve]

- Secondary 1** - proportion of patients achieving an ASAS40 response in overall population [ASAS40 overall]
Secondary 2 - proportion of patients achieving an ASAS20 response in overall population [ASAS20]
Secondary 3 - change from baseline in ASDAS score in overall population [ASDAS CFB]
Secondary 4 - change from baseline in BASDAI in overall population [BASDAI CFB]
Secondary 5 - change from baseline in BASFI in overall population [BASFI CFB]
Secondary 6 - proportion of patients achieving ASDAS<2.1 in overall population [ASDAS<2.1]
Secondary 7 - change from baseline in MRI of the spine in overall population [MRI spine CFB]
Secondary 8 - change from baseline in SF-36 PCS score in overall population [SF-36 PCS CFB].

A graphical multiple testing procedure (Bretz et al. 2011) will be used to control the family-wise type I error rate at a 2-sided α level of 0.05. The graphical approach is a closed testing procedure; hence, it strongly controls the family-wise error rate (Alosh et al. 2014). Each hypothesis is represented as a node in a graph. Directed arrows between the nodes with associated weights represent how alpha is passed from its initial allocation to other nodes. The testing scheme will be fully specified by the graph (including nodes, arrows and weights) along with the initial alpha allocation. Figure RHCH.6. 1 shows the graphical testing scheme with initial α allocation and weights. Unless otherwise specified, there will be no adjustment for multiple comparisons for any other analyses..

[figure not shown]

Figure RHCH.6. 1 Illustration of graphical multiple testing procedure with initial α allocation and weights.

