Ankylosing Spondylitis Disease Activity Score (ASDAS): The ASDAS is a composite index to assess disease activity in AS (Machado et al. 2011a, 2011b; Zochling 2011). The parameters used for the ASDAS (with CRP as acute phase reactant): 1) Total back pain (BASDAI Q2) 2) Patient global 3) Peripheral pain/swelling (BASDAI Q3) 4) Duration of morning stiffness (BASDAI Q6) 5) CRP in mg/L	ASDAS _{crp} ASDAS _{crp} change from baseline - major secondary outcome	ASDAS _{crp} (Sieper et al. 2009): $0.121 \times \text{total back pain} + 0.110 \times \text{patient global} + 0.073 \times \text{peripheral pain/swelling} + 0.058 \times \text{duration of morning stiffness} + 0.579 \times \text{Ln}(\text{CRP}+1)$ (Machado et al. 2015). C-reactive protein is in mg/liter, the range of other variables is from 0 to 10; Ln represents the natural logarithm.	Missing if any of the components is missing. If CRP <2 mg/L or below the limit of detection, then use 2 mg/L in the calculation (Machado et al. 2015).

Measure / Description	Variable	Derivation / Comment	Imputation Approach if with Missing Components
	ASDAS Disease Activity States	Four (4) disease activity states have been defined by ASAS consensus (Machado et al. 2011c, Machado 2018): 
 • ASDAS <1.3 defines inactive disease • $1.3 \leq \text{ASDAS} < 2.1$ defines low disease activity • $2.1 \leq \text{ASDAS} \leq 3.5$ defines high disease activity • ASDAS >3.5 defines very high disease activity. 	Set the disease activity state to worst state (ie, very high) if observed ASDAS score is missing
	ASDAS<2.1	Defined as ASDAS <2.1 (low or inactive disease activity)	
	Clinical important improvement	Defined as at least 1.1 unit change in ASDAS from baseline	Missing if baseline or observed ASDAS score is missing
	Major improvement	Defined as at least 2.0 unit change in ASDAS from baseline or reached the minimum of ASDAS score (0.6361) at postbaseline visit	

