Maastricht Ankylosing Spondylitis Enthesitis Score (MASES): The MASES is an index used to measure the severity of enthesitis (Heuft-Dorenbosch et al. 2003). The MASES assesses 13 sites for enthesitis using a score of “0” for no activity, or “1” for activity. Sites assessed include: costochondral 1 (right/left), costochondral 7 (right/left), spinal iliaca anterior superior (right/left), crista iliaca (right/left), spinal iliaca posterior (right/left), processus spinosus L5, and Achilles tendon proximal insertion (right/left).	MASES	The MASES is the sum of all site scores. Range: 0 to 13, higher scores indicate more severe enthesitis 0 = no activity and not evaluable 1 = activity	Missing if >20% (ie, ≥3) sites are missing. If ≤20% missing, then imputed sum = sum of scores from nonmissing sites x 13/ no. of nonmissing sites
	MASES score = 0	MASES score = 0 refers to complete resolution in enthesitis. Analysis of MASES score = 0 only applies to patients with baseline enthesitis (MASES >0).	Missing if observed value is missing
	Heel Enthesitis score = 0	Heel Enthesitis score = 0 refers to Achilles tendon proximal insertion (right/left) = 0. Analysis of Heel Enthesitis score = 0 only applies to patients with baseline Heel Enthesitis score >0.	Missing if observed value is missing

Measure / Description	Variable	Derivation / Comment	Imputation Approach if with Missing Components
Non-Steroidal Anti-Inflammatory Drug (NSAID) Intake: Information regarding NSAIDs (including COX-2 inhibitors) intake will be collected in the eCRF and the ASAS-NSAID score will be calculated (Dougados et al. 2011).	Proportion of patients taking NSAID	Proportion of patients taking NSAID (including COX-2 inhibitors) at specified visit	NA
	ASAS -NSAID score	See Section 6.9.4.1 and Appendix 2 for details of deriving ASAS-NSAID score. ASAS-NSAID = 0 if no NSAID use	If NSAID dose is missing, the maximum efficacy dose (Appendix 2) is assumed. If frequency is missing, 'every day' intake is assumed.
	ASAS-NSAID50	$100 \times \frac{\text{Baseline ASAS-NSAID} - \text{Observed ASAS-NSAID}}{\text{Baseline ASAS-NSAID}}$ Proportion of patients with at least 50% decrease from baseline in ASAS-NSAID score. Derivation only applies to patients whose ASAS-NSAID is not equal to 0 at baseline.	
	ASAS-NSAID 10	Proportion of patients with ASAS-NSAID score <10	
	ASAS-NSAID 0	Proportion of patients with ASAS-NSAID score = 0	

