6.9.2. Major Secondary Efficacy Analyses

The major secondary outcomes at Week 16 (Visit 8) are:

- Proportion of patients achieving an ASAS40 response in overall population
- Proportion of patients achieving an ASAS20 response in overall population
- Change from baseline in ASDAS in overall population
- Change from baseline in BASDAI in overall population
- Change from baseline in BASFI in overall population
- Proportion of patients achieving ASDAS < 2.1 in overall population
- Change from baseline in MRI SPARCC spine score in overall population
- Change from baseline in SF-36 PCS in overall population*

* Detailed descriptions and analyses on SF-36 PCS are described in Table RHCH.6.5 and Table RHCH.6.6.

The major secondary analysis will be based on the ITT Population for Period 2 comparing the ixekizumab treatment group and placebo at Week 16 (Visit 8).

The primary analysis for categorical major secondary outcomes is a logistic regression analysis with treatment, baseline CRP status and TNF inhibitor experience in the model (only in overall population, Section 6.1.1). Missing data will be imputed using the NRI method (Section 6.3.1).

The primary analysis for continuous major secondary outcomes (except MRI SPARCC spine score) is an MMRM analysis with treatment, baseline CRP status, TNF inhibitor experience, baseline value, visit, baseline value-by-visit, and treatment-by-visit interaction as fixed factors (Section 6.1.1).

The primary analysis for change from baseline in MRI SPARCC spine score is an observed case analysis using ANCOVA with treatment, baseline CRP status, TNF inhibitor experience, and baseline value in the model (Section 6.1.1). Only patients with both baseline and Week 16 SPARCC spine score will be included in the analysis.

These major secondary comparisons will be tested based on the graphical multiple testing procedure detailed in Section 6.4.

Table RHCH.6.4 provides the detailed analyses including analysis type, method and imputation, population, time point, and treatment comparisons for major secondary outcomes.

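### The alpha-controlled analysis of ASDAS <2.1 omits baseline ASDAS, and its time-to-first analysis counts the few patients already below 2.1 at entry as early events

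*SAP*

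**What the plan says.** SAP 6.4 lists Secondary 6 as "proportion of patients achieving ASDAS<2.1 in overall population [ASDAS<2.1" at Week 16, within a graphical procedure meant to "control the family-wise type I error rate at a 2-sided α level of 0.05". Table RHCH.6.3 gives the definition "Defined as ASDAS <2.1 (low or inactive disease activity", with no condition on improvement or on the starting value. SAP 6.9.2 specifies "a logistic regression analysis with treatment, baseline CRP status and TNF inhibitor experience in the model" for the categorical major secondary outcomes, with nonresponder imputation in the ITT Population.

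Protocol 6.1 sets the activity criterion: "Have active r-axSpA defined as BASDAI ≥ 4 and total back pain ≥ 4". It sets no ASDAS minimum. On CRP it says "Biologic naïve patient would be enrolled regardless of the CRP level". SAP 5.2 plans for "approximately 40% of patients with non-elevated baseline CRP", meaning 5.00 mg/L or less.

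The SAP handles related outcomes differently. ASDAS change is modelled with the baseline value and its interaction with visit (SAP 6.1.1 and 6.9.2). For complete resolution of enthesitis, Table RHCH.6.3 says "Analysis of MASES score = 0 only applies to patients with baseline enthesitis (MASES >0". Table RHCH.6.4 also plans a Kaplan-Meier analysis of time to first ASDAS <2.1 in the whole ITT Population. Under SAP 6.1.1 that time runs from randomization to the first visit in Period 2 at which the criterion is met.

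**The concern.** Whether a patient is below a fixed ASDAS threshold at Week 16 plausibly depends on where that patient started. Binary CRP status stands in for only part of that, since CRP is one of five ASDAS components. Leaving out a baseline value that is already collected may give up some power on a confirmatory endpoint.

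The entry rule and the endpoint also measure different things. BASDAI counts fatigue, enthesitis and stiffness intensity; ASDAS does not, and it adds patient global and CRP. A patient can therefore be active by the entry rule and already below 2.1 by ASDAS. If unchanged, that patient counts as having achieved the endpoint at Week 16. In the time-to-first analysis the same patient is an event at Week 1, although nothing began at Week 1.

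**Working it through.** **Inputs.** From SAP Table RHCH.6.3:

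- ASDAS = 0.121×Q2 + 0.110×global + 0.073×Q3 + 0.058×Q6 + 0.579×ln(CRP+1), with CRP below 2 mg/L set to 2.
- BASDAI = (Q1 + Q2 + Q3 + Q4 + (Q5+Q6)/2)/5.
- Protocol 9.1.2.9 has the same ASDAS form with coefficients 0.1216, 0.1106, 0.0736, 0.0586 and 0.5796.

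**The SAP's own figure.** With every item at 0 and CRP at the floor, ASDAS = 0.579×ln 3 = 0.6361. This matches the minimum printed in the table. The documents give no assumed rate or power for ASDAS <2.1.

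**Can an eligible patient start below 2.1?**

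| Profile | BASDAI | ASDAS (SAP) |
|---|---|---|
| All items 4, global 4, CRP ≤2 | 4.0 | 4×0.362 + 0.636 = 2.084 |
| Q1–Q6 = 5, 4, 2, 5, 4, 4; global 4; CRP ≤2 | 4.0 | 0.484 + 0.440 + 0.146 + 0.232 + 0.636 = 1.938 |
| Q1–Q6 = 7, 4, 1, 5, 6, 3; global 4; CRP ≤2 | 4.3 | 0.484 + 0.440 + 0.073 + 0.174 + 0.636 = 1.807 |
| Q1–Q6 = 6, 4, 0, 6, 4, 4; global 3; CRP 5 | 4.0 | 0.484 + 0.330 + 0 + 0.232 + 1.037 = 2.083 |

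So it is possible. With the protocol coefficients and CRP 2, the first profile scores 4×0.3644 + 0.637 = 2.094, still below 2.1. Entry bounds the Spinal Pain item rather than BASDAI Q2, so setting Q2 to 4 is cautious.

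**How much does CRP matter?** The all-4 patient stays below 2.1 only while CRP < exp((2.1 − 1.448)/0.579) − 1 = 2.08 mg/L. At CRP 5 the score is 1.448 + 1.037 = 2.485. Non-elevated CRP alone is therefore not enough.

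**How many patients?** The documents give no baseline ASDAS distribution, so this part is assumption. Correlated 0–10 items were simulated (SD 2, correlation 0.5, peripheral item 2 points lower), with CRP uniform on 0.2–5 in the 40% non-elevated group and the entry rule applied.

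- Mean BASDAI after entry ran from 5.3 to 6.4.
- The share below 2.1 ran from 2.9% down to 0.8% of all patients, and from 7.2% down to 1.9% of the non-elevated group. It was nil in the elevated group.
- Other assumed distributions gave 0.6% to 1.3% overall.

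Taking 0.5% to 3%: 0.005×140 = 0.7 and 0.03×140 = 4.2, or about 1 to 4 patients.

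**Dilution.** Assume 40% versus 12% among patients who start at or above 2.1, a difference of 28 points. Suppose 3% start below it.

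- Assumed rates of 85% versus 70% in that 3%: 0.97×28 + 0.03×15 = 27.6, a loss of 0.4 points.
- No difference at all between arms in that 3%: 0.97×28 = 27.2, a loss of 0.8 points.

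**Gain from the covariate.** The figures below come from simulated trials with 70 per arm, assumed residual SD 0.85 and 1,500 trials per scenario. The slope is that of Week 16 ASDAS on baseline ASDAS. The rates 42% versus 15% are borrowed from the ASAS40 assumptions in Protocol 10.1.

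| Slope | 42% v 15%, without → with | 40% v 20%, without → with |
|---|---|---|
| 0.3 | 95.4% → 95.5% | 73.0% → 74.4% |
| 0.5 | 95.3% → 96.1% | 75.1% → 77.3% |
| 0.7 | 95.9% → 96.8% | 76.6% → 80.1% |

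The simulation standard error of a single power figure is about √(0.75×0.25/1500) = 1.1 points near 75%, and √(0.955×0.045/1500) = 0.5 points near 95.5%. The smallest gains should be read as roughly nil. With slopes from 0.3 to 0.9, the ranges are about 0 to 2 points and 0 to 5 points respectively.

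**The case against.** Several points on the other side stand.

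- **Validity.** Randomization is stratified by CRP status and TNF inhibitor experience, and both are in the model. Patients already below 2.1 can fall in either arm. Type I error is not inflated.
- **Meaning of the endpoint.** ASDAS <2.1 is a disease-activity state defined for every patient. Resolution of enthesitis has no meaning without baseline enthesitis, so that restriction is an imperfect precedent and gives no reason to shrink the confirmatory denominator.
- **Other evidence.** ASDAS change is itself alpha-controlled (Secondary 3) and baseline-adjusted, and improvements of at least 1.1 and 2.0 are analysed. No reader has to judge change from ASDAS <2.1 alone.
- **Status of the time-to-first analysis.** It is supportive and outside the error control.

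A reader might also infer from the ASDAS categories below 2.1 in the baseline characteristics table (SAP 6.6.1) that the sponsor expects such patients. The table does not show this: it also lists BASDAI below 4, which entry excludes, so the categories are generic. The table will, however, display how many patients start below 2.1.

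SAP 6.9.6 allows extra covariates as exploratory analyses. This is only a partial answer. It does not name baseline ASDAS, and a covariate chosen after unblinding cannot serve a confirmatory test.

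**Conclusion.** The point holds at modest weight. An alpha-controlled state endpoint is modelled without its own baseline value, and its time-to-first analysis can record events that are not onsets. That second defect follows from the definitions, whatever the number of patients. The first is a matter of efficiency.

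Three stronger readings go too far. The planned 40% with non-elevated CRP does not mean that 40% are exposed: the all-4 patient needs CRP near or below 2 mg/L, and the simulated share is about 0.5% to 3% of all patients. The endpoint is not invalid or biased. A large loss of power is not shown either. A gain of about 12 points (59.5% to 71.3%) appeared only with a slope of 0.9, response rates in the region of 37–43% versus 18–24%, and a model without the TNF inhibitor term. Nothing in the documents supports that slope or those rates.

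The eligible profiles are exact arithmetic. The share of patients, the dilution and the power gain all rest on the assumed distributions, rates and slopes shown above.

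**What to change.** Before unblinding, amend the SAP as follows.

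1. Add continuous baseline ASDAS to the logistic regression for ASDAS <2.1, and to that for ASDAS inactive disease. Keep all ITT patients in the denominator for the alpha-controlled test, and still report the treatment difference already planned in SAP 6.1.1.
2. Restrict the time-to-first ASDAS <2.1 analysis to patients with baseline ASDAS of at least 2.1.
3. Add one supportive response-rate analysis in that same subset.

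The cost is SAP wording; the baseline value is already collected. The one statistical consequence to state is that the odds ratio becomes conditional on baseline ASDAS, so it is not directly comparable with one from the model as now written.

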9.1.2.10. Maastricht Ankylosing Spondylitis Enthesitis Score

The MASES is an index used to measure the severity of enthesitis (Heuft-Dorenbosch et al. 2003). The MASES assesses 13 sites for enthesitis using a score of “0” for no activity or “1” for activity. Sites assessed include costochondral 1 (right/left), costochondral 7 (right/left), spinal iliaca anterior superior (right/left), crista iliaca (right/left), spina iliaca posterior (right/left), processus spinosus L5, and Achilles tendon proximal insertion (right/left). The MASES is the sum of all site scores (range 0 to 13); higher scores indicate more severe enthesitis.

The MASES must be assessed by a rheumatologist or health care provider who meets the qualifications for study assessments.

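### The SAP scores an enthesitis site that could not be examined as 0, which can create a false heel response or a false MASES of 0 and sits unexplained beside the missing-site rule in the same row

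*SAP*

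**What the plan says.** Protocol section 9.1.2.10 gives each site two possible values: "The MASES assesses 13 sites for enthesitis using a score of “0” for no activity or “1” for activity". It does not mention a site that cannot be evaluated.

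SAP section 6.9, Table RHCH.6.3, repeats the 13 sites and the 0-to-13 range and states that "The MASES is the sum of all site scores". Its derivation cell then adds a third state to the zero code: "0 = no activity and not evaluable".

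The imputation cell of the same row sets two rules for missing sites:
- One or two sites lost, where the total is scaled up: "If ≤20% missing, then imputed sum = sum of scores from nonmissing sites x 13/ no. of nonmissing sites".
- Three or more sites lost, where no total is given: "Missing if >20% (ie, ≥3) sites are missing".

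Two binary endpoints follow: "MASES score = 0 refers to complete resolution in enthesitis", restricted to patients with baseline MASES above 0, and "Heel Enthesitis score = 0 refers to Achilles tendon proximal insertion (right/left) = 0", restricted to patients with a baseline heel score above 0. For both, the only missing-data instruction is that the response is missing when the observed value is missing. SAP section 6.3.1 turns a missing response into nonresponse (NRI).

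Table RHCH.6.4 analyses change in MASES by MMRM, and the two binary endpoints by logistic regression and Fisher's exact test with NRI. It also summarises all three descriptively in Period 3. All are other secondary analyses, which SAP section 6.9.4 leaves without multiplicity adjustment.

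**The concern.** A site that was not examined carries no information about enthesitis, yet the code gives it the best possible value. The neighbouring cell handles an unassessed site in the opposite way, by scaling up or by withholding the total, and the SAP does not say how non-evaluable differs from missing. A programmer following the text would score two kinds of unassessed site in opposite ways.

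This is also out of step with the rest of the SAP. BASMI averages the measurements that are present, ASAS-HI reduces its denominator for items that do not apply, and a missing ASDAS is assigned the worst activity state.

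What is at stake is the size of the MASES total and, more directly, who counts as a responder on the two zero-score endpoints. The heel endpoint is the most exposed because it rests on only two sites.

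**Working it through.** **Inputs.** From SAP Table RHCH.6.3: 13 sites, the zero code, the proration formula and the threshold of three sites. From SAP section 6.3.1: NRI. The documents give no frequency of non-evaluable sites, so the check concerns single patients.

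**The plan's own figure.** 1/13 = 7.7%, 2/13 = 15.4%, 3/13 = 23.1%. The smallest count above 20% is three, which matches the SAP.

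**Totals after baseline.** Let A be the number of active sites among those examined and m the number non-evaluable.
- Scored as 0: total = A.
- Treated as missing: total = A × 13/(13 − m) for m = 1 or 2; missing for m ≥ 3.

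For A > 0 the ratio of the first to the second is (13 − m)/13: 12/13 for one site (7.7% lower) and 11/13 for two (15.4% lower).

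| A | Scored as 0 | m = 1 prorated | m = 2 prorated | m ≥ 3 |
|---|---|---|---|---|
| 4 | 4 | 4 × 13/12 = 4.33 | 4 × 13/11 = 4.73 | missing |
| 6 | 6 | 6 × 13/12 = 6.50 | 6 × 13/11 = 7.09 | missing |
| 0 | 0 | 0 × 13/12 = 0 | 0 × 13/11 = 0 | missing |

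**MASES = 0.** The last row shows where the two rules part. With one or two non-evaluable sites and nothing else active, both give 0 and both count as resolution. With three or more, the zero code gives resolution, while the missing rule gives no total and therefore nonresponse under NRI.

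**Heel = 0.** Take a patient whose active Achilles sites at baseline cannot be examined later, with any other Achilles site at 0. The zero code gives a heel score of 0 and a response. If the heel score were missing, NRI would make the patient a nonresponder.

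**Direction.** Illustrative patients, one non-evaluable site:
- *Week 16 only:* baseline 6; 4 active at Week 16. Improvement is 6 − 4 = 2 as coded, against 6 − 4.33 = 1.67 prorated. The code overstates.
- *Baseline only:* 4 active at baseline; Week 16 score 2. Improvement is 4 − 2 = 2 as coded, against 4.33 − 2 = 2.33 prorated. The code understates.
- *Both visits:* 6 active, then 4. Improvement is 2 as coded, against 6.50 − 4.33 = 2.17 prorated. The code understates.

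In addition, a patient whose only active sites are non-evaluable at baseline scores 0 and drops out of the MASES > 0 or heel > 0 analysis set.

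**The case against.** The strongest reply is that the SAP names two states, non-evaluable and missing, and that a case report form could record them separately. Both rules could then run without conflict. The protocol is silent on non-evaluable sites and leaves analysis detail to the SAP, so the SAP fills a gap and does not contradict the protocol. This stands as far as it goes. It does not give a reason for scoring one kind of unassessed site as healthy, and followed as written the rule still produces the false heel response.

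It can also be said that proration is itself an imputation, which assumes unexamined sites are active at the same rate as examined ones. That is right: 7.7% and 15.4% are differences between two conventions, not measured errors.

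Two stronger readings are tempting, and the documents do not support either. A reader might infer that the code always favours improvement, or favours ixekizumab. It applies at baseline as well, where it works the other way, and it applies identically in both blinded arms. A reader might also infer that a patient whose single active site becomes non-evaluable would be a nonresponder on MASES = 0 if only the site were coded missing. Under the SAP's own proration that total stays at 0, so NRI is not triggered.

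**Conclusion.** The rule is wrong as written, with limited reach. After baseline, with other sites active, it lowers MASES by 7.7% or 15.4% relative to proration for one or two non-evaluable sites. It misclassifies response in two situations: heel = 0 when Achilles sites active at baseline cannot be examined, and MASES = 0 when three or more sites are non-evaluable and no examined site is active. At baseline it lowers the score and can remove patients from the analysis sets, so no overall direction of bias can be claimed.

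The conclusion assumes that a non-evaluable site is one whose enthesitis status was not determined. The effect on results cannot be sized, because the frequency of such sites is not given. The primary and major secondary endpoints are untouched. This is a small correction worth making, not a threat to the trial's main conclusions.

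**What to change.** In Table RHCH.6.3, replace the code with: *0 = no activity; 1 = activity; not evaluable = missing*. The stated proration and three-site rule then apply to the total.

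For heel = 0, add that the response is missing, and so a nonresponse under NRI, if an Achilles site active at baseline is not evaluable at the visit.

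Because proration leaves a zero sum at zero, put the same condition on MASES = 0: every site active at baseline must be evaluable, otherwise the response is missing and NRI applies.

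The recode will not bring back patients whose only active sites were non-evaluable at baseline. Their score would be 0 or missing, and they would stay outside the analysis set.

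The cost is a few lines of SAP text, derivation code that links each site to its baseline value, and slightly lower resolution rates. The change should be made before the Week 16 lock and unblinding.
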